Study protocol

Title:	From short-term surgical missions towards sustainable partnerships A survey among members of foreign teams and local doctors involved in surgical missions.
Study Protocol number:	2019-05
Date of protocol approval:	May 15 th 2019, by the board of Global Surgery Amsterdam
Study type:	Survey The content of the survey is provided below in this study protocol
Initiating organization:	Global Surgery Amsterdam (GSA) www.globalsurgeryamsterdam.com
Collaborating organization:	ICOPLAST www.icoplast.org
General information:	Particularly in low- and middle-income countries (LMICs), surgical missions are conducted on a large scale to provide surgical care. Annually, an estimated 313 million US dollars is spent on surgical missions. Typical missions are short-term, lasting up to several weeks. However, currently we know very little about the actual impact of these missions, including patient outcomes and strategies to make missions more sustainable. Therefore we developed an online survey. It is a first step in identifying what is currently being done and what should be done according to the respondent's experiences. The answers are used to provide more clarity on today's practices of short-term missions and to provide recommendations for the future. The survey consists of 21 questions. Outcomes will be anonymized.
Participants:	Members of foreign teams and local doctors involved in surgical missions.
Start of distribution:	June 2019, by email within the network of GSA and ICOPLAST
End of enrollment:	October 2019
Ethical clearance:	Not required for this study type

A survey for international and local team members involved in surgical missions in LMICs.

Developed by ICOPLAST and Global Surgery Amsterdam

www.icoplast.org

www.globalsurgeryamsterdam.com

Background:

We all aim for improving outcomes of our patients all around the globe. Many of our patients suffer from conditions that can be treated with (reconstructive) surgery. Particularly in low- and middle-income countries, surgical missions are conducted on a large scale to provide this type of care. Annually, an estimated 313 million US dollars is spent on surgical missions. Typical missions are short-term, lasting up to several weeks.

However, currently we know very little about the actual impact of these missions, including patient outcomes and future strategies (Hendriks et al., 2019).

Therefore we developed this questionnaire. It is a first step in identifying what is currently being done and what should be done, according to your valuable experiences in the field. Your data is used to provide more clarity on today's practices of short-term missions.

The questionnaire consists of 21 questions. Please select one answer, and further clarify in the comment box if applicable.

Note: we may ask additional questions in the future if you approve us to contact you.

Outcomes will be anonymized.

Your function *

- Nurse / physician assistant (Please specify below)
- Plastic surgeon
- Orthopedic surgeon
- General surgeon
- Other surgeon (Please specify below)
- Policy officer NGO (Please specify below)
- Board member NGO
- Other...

Q1. Name *

Short answer text

Q2. Age: *

Short answer text

Q3. Sex: *

Short answer text

Q4. Email address: *

Short answer text

Q5. Nationality: *

Short answer text

Q6. How many missions did you perform in your life? *

Short answer text

Q7. Country where you performed your last surgical mission: *

Short answer text

Q8. Name of the hospital and town: *

Short answer text

Q9. Name of the NGO that supported this mission: *

Short answer text

Q10. Country where this NGO is based: *

Short answer text

Q11. Please give points over the following potential activities of a visiting team
(more points means a more important activity) *

	1 point	2 points	3 points	4 points
Provide surgical equipment and consumables for the local team, also for use after the mission left				
Provide free treatments				
Treat patients yourself				
Facilitate teaching of local staff (doctors and/or nurses)				

Q12. Is there, in your opinion, an activity missing in question 11? (please explain what activity is important and why) *

Long answer text

Q13. Should medical registration in the host country be required for specialists performing short-term surgical missions? *

- Strongly agree
- Agree
- Neither agree or disagree
- Disagree
- Strongly disagree

Comments:

Long answer text

Q14. When medical registration was required for your last mission, the process to obtain the documents was straightforward. *

- Strongly agree
- Agree
- Neither agree or disagree
- Disagree
- Strongly disagree

Comments:

Long answer text

Q15. What can you say about the collaboration between authorities in LMICs (like the Ministry of * Health, the district health management or the national surgical society) and visiting surgical teams?

- There is no collaboration and it should be developed as a priority
- Collaboration is present but improvement is needed
- Collaboration has no benefits nor disadvantages
- Collaboration will likely be more harmful than beneficial for the mission

Comments:

Long answer text

Q16. What should have a higher priority in the hospital of your last mission ? Teaching in anesthesia care or teaching in surgical care?

*

- Anesthesia care
- Reconstructive care
- General surgical care
- Other surgical care (please specify in comments)

Comments:

Long answer text

Q17. A structured follow-up strategy (>6 months) of patients is required for short-term surgical missions.

- Strongly agree
- Agree
- Neither agree nor disagree
- Disagree
- Strongly disagree

Comments:

Long answer text

Q18. One month after the mission, an official report on the outcome including all complications encountered is recommended for all surgical missions. *

- Strongly agree
- Agree
- Neither agree nor disagree
- Disagree
- Strongly disagree

Comments:

Long answer text

Q19. A written long-term strategy (>5 years) with clear goals, developed by the visiting team and the local actors together, is recommended at the start of a new project. *

- Strongly agree
- Agree
- Neither agree nor disagree
- Disagree
- Strongly disagree

Comments:

Long answer text

Q20. What would you suggest to improve the impact of short term surgical missions? *

Long answer text

Q21. Hereby I give consent to use this data for publication. The purpose of this publication is to provide more insight into short-term surgical missions

Yes

No

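### The protocol states its survey population in two inconsistent ways, and no item confirms involvement in a mission before the last-mission questions, two of which have no not-applicable option

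*Protocol*

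**What the plan says.** The population is described in two places. The Title and the Participants row name "members of foreign teams and local doctors involved in surgical missions". The heading above the questionnaire calls it "A survey for international and local team members involved in surgical missions in LMICs".

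The form opens with a list of functions. Besides four kinds of surgeon it offers "Nurse / physician assistant (Please specify below"), "Policy officer NGO (Please specify below"), "Board member NGO" and an open category. Distribution is given as "June 2019, by email within the network of GSA and ICOPLAST", with no stated restriction to people who have been involved in a mission.

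The only item that counts mission experience is "Q6. How many missions did you perform in your life". It is free text, and no minimum, skip or exclusion is attached to it. The starred items Q7 to Q10 then ask about the last mission: its country, its hospital and town, the supporting NGO and where that NGO is based. Q14 (ease of obtaining registration) and Q16 (teaching priority in that hospital) are also starred and also refer to the last mission. Q14 has five answers on an agreement scale and Q16 has four. Neither has a not-applicable choice, though each has a comment box.

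**The concern.** The survey is meant to report practice and recommendations from respondents' own experience in the field. That needs a clear rule on whose form counts, and some assurance that answers about a last mission come from people who had one. The protocol provides neither in full.

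Two things are at stake. First, whether a completed form from a local nurse or physician assistant belongs in the survey depends on which line of the protocol is followed. Second, a respondent with no mission can reach Q14 and Q16 and leave an answer there that looks the same as a participant's answer. The questionnaire is fixed in this protocol, so an analysis plan written later can work only with what the form recorded.

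**Working it through.** No sample size, power or rate is stated and the point depends on none, so the check is a comparison of texts.

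**Step 1. Apply both population statements to typical respondents.**

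| Respondent | Title and Participants row | Survey heading | Function list |
|---|---|---|---|
| Foreign surgeon or nurse on a team in an LMIC | in | in | accepted |
| Local doctor working with a team in an LMIC | in | in | accepted |
| Local nurse working with a team in an LMIC | out (local side is doctors only) | in | accepted |
| Foreign team member, mission outside an LMIC | in | out | accepted |
| NGO officer travelling with a foreign team in an LMIC | in | in | accepted |
| NGO officer who has never been on a mission | out | out | accepted |

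Rows three and four show the inconsistency between the two statements. The last row shows that the form admits people whom both statements leave out. Row four matters less, because the General information row already centres on LMICs and Q7 records the country.

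**Step 2. Count the function options.** Four surgical, one nurse or physician assistant, two NGO, one open: 4 + 1 + 2 + 1 = 8. The two NGO options and the open one (3 of 8) need not describe a team member or a local doctor.

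**Step 3. Count the items that presuppose a mission.** Q7, Q14 and Q16 name the last mission; Q8, Q9 and Q10 refer back to it: 3 + 3 = 6 starred items. Four (Q7 to Q10) are free text, so a respondent can write that there was none. Two (Q14, Q16) are closed and allow no such answer on the scale itself.

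**Step 4. Follow one respondent through the form.** An NGO policy officer on the mailing list with no mission enters 0 at Q6. Nothing follows from that entry. At Q14 the nearest choice is the neutral midpoint, which cannot be told from a participant's neutral view. At Q16 any choice reads as a stated priority for a hospital that the respondent never worked in.

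**Step 5. Ask what can be recovered afterwards.** Q6 asks "How many missions did you perform in your life". A local doctor or nurse who hosted visiting teams may fairly enter 0, so dropping the zeros could remove part of the intended population. Reading Q6 with Q7 to Q10 helps: someone who enters 0 but names a hospital and an NGO probably took part, and someone who writes none throughout did not. This sorts many respondents, but it is a judgement on free text. Q7 also asks where the respondent performed the mission, so it carries the same difficulty for local staff.

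**The case against.** The strongest case on the other side has four parts.

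- **There are two written definitions, not three.** A reader might count the function list as a third conflicting definition. It is an occupation question, not an eligibility rule. Both written statements share the criterion of involvement in surgical missions, and an NGO officer who travels with a team fits both. This stands: the officer with no mission is already outside the stated population, and what is missing is a step that enforces it.
- **Pooling is not stated.** A reader might infer that non-participants are merged with field participants in the agreement shares for Q13 and Q17 to Q19. The protocol describes no analysis, and a plan that is not shown may separate them. Those four items also ask for opinion on what ought to happen, which NGO staff involved in missions can properly give. This stands.
- **The star is not defined.** A reader might say that respondents are forced to answer. That is a reasonable inference, because the star is used selectively (Q17 and Q21 have none), but it remains an inference. Q14 is also worded conditionally, and the comment boxes let a respondent explain.
- **The form is not blind to participation.** Function and Q6 to Q10 are all collected, so it is too strong to say that non-participants cannot be found.

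These arguments narrow the point without removing it. A comment beside Q14 or Q16 does not undo the scale answer, and a neutral midpoint is not a not-applicable answer. The local-nurse conflict is untouched by any of them.

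**Conclusion.** The concern holds in a limited form. The protocol contradicts itself on local non-doctors and on the LMIC restriction, its function list is wider than either statement, and nothing confirms involvement before the six last-mission items. At Q14 and Q16, answers with no mission behind them can be recorded as substantive, and Q6 with Q7 to Q10 allows only partial identification afterwards.

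The size is unknown. The protocol gives no figure for how many people in the two networks have never been on a mission, how many respondents are local non-doctors, or how their answers differ, so neither the amount nor the direction of any distortion can be derived. The conclusion rests on two assumptions: that some recipients of the email have no mission experience, and that some of them would tick an answer at Q14 or Q16. It does not require that the star makes an item compulsory, nor that answers are pooled. This is a cheap improvement worth making, not a defect that invalidates the survey.

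**What to change.** 1. Use one population definition in the Title, the Participants row and the survey heading. State whether local non-doctors and NGO staff without field involvement are included, and whether the setting is limited to LMICs.
2. Add a first item asking whether the respondent has personally taken part in at least one surgical mission in an LMIC, as a visiting team member or as local staff.
3. Route those who answer no past Q6 to Q10, Q14 and Q16, and report them separately.
4. Add a not-applicable choice to Q14 and Q16. At Q14 this also serves participants whose last mission required no registration.

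Two further changes are optional: asking profession and NGO role as separate items, and wording Q6 and Q7 in terms of taking part instead of performing, so that they fit local staff.

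The cost is one extra item, a skip rule in the online form, two answer choices and aligned wording. The denominators for Q14 and Q16 will be slightly smaller. If forms have already been collected, items 2 to 4 no longer apply to them. In that case, write down a rule for classifying participants from Q6 to Q10, apply it before looking at the other answers, and report the unclassifiable forms as a group of their own.

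### Follow-up, outcome reporting and long-term strategy are asked only as norms, and Q14 has no answer for respondents who needed no registration, so current practice is only partly measured

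*Protocol*

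**What the plan says.** The protocol's General information row gives a double aim: "It is a first step in identifying what is currently being done and what should be done according to the respondent's experiences". It then says how the answers will be used: "The answers are used to provide more clarity on today's practices of short-term missions and to provide recommendations for the future". The introduction that respondents read repeats the first part of that: "Your data is used to provide more clarity on today's practices of short-term missions". The questionnaire is printed in the protocol, so its items and answer options are fixed there.

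The form collects some facts. Q6 asks for a lifetime count of missions. Q7 to Q10 ask for the country, hospital and town, NGO and NGO home country of the last mission; Q7, for example, reads "Country where you performed your last surgical mission". Q14 concerns registration at the last mission, and Q15 concerns collaboration between authorities and visiting teams.

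Q17, Q18 and Q19 each present a statement that something is required or recommended, with five options from strong agreement to strong disagreement. Q13 asks on the same kind of scale whether host-country registration ought to be required. Q14 then asks, for the case where it was required, whether getting the documents was straightforward; it has the same five options and carries an asterisk. Comment boxes follow Q13 to Q19, to be used where applicable. The introduction also says "we may ask additional questions in the future if you approve us to contact you".

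**The concern.** Agreement that follow-up, reporting or a long-term strategy ought to exist does not show that it existed. A group could endorse all three almost unanimously and practise none of them, or the reverse. If the report then describes high agreement as clarity on present practice, that claim has no closed data behind it. This is not something a statistical analysis plan could settle, because analysis cannot supply answers to questions that the form does not ask.

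Q14 has a different fault. Its wording is conditional, but the answers do not identify who meets the condition. A respondent whose last mission needed no registration has no fitting option. If that respondent chooses one of the five anyway, the distribution of ease combines people who went through the process with people who did not, in unknown proportion.

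**Working it through.** No sample size, error rate or power figure is stated or needed. The check is a reading of the items, plus one illustration for Q14.

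**Step 1: classify the mission-related items, Q6 to Q20 (15 items).**
- Mission facts: Q6, Q7, Q8, Q9, Q10 = 5.
- Touching practice: Q14 and Q15 = 2.
- Opinion or norm: Q11, Q12, Q13, Q16, Q17, Q18, Q19, Q20 = 8.
- Check: 5 + 2 + 8 = 15. Opinion share: 8/15 = 53%.

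**Step 2: set the three norm items against the practice half of the aim.**

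| Item | Topic | What the closed answer records | Closed item on whether it happened |
|---|---|---|---|
| Q17 | Structured patient follow-up, >6 months | Agreement that it is required | None |
| Q18 | Official report with complications, one month after | Agreement that it is recommended | None |
| Q19 | Joint written strategy, >5 years | Agreement that it is recommended | None |

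The present tense of Q17 could be read as a statement of fact about current requirements. Even so, agreement would not record whether follow-up took place.

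**Step 3: look for a way to isolate the right respondents in Q14.**
- Options meaning that registration was not required: 0 of 5.
- Filter question: none. Q13, the item before it, asks for an opinion, so its answer does not show whether registration was required at the last mission.
- Asterisk: present on Q14, absent from the comment boxes. That fits a required answer, but the document does not define the sign.

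**Step 4: illustrate what mixing could do to Q14.** All inputs here are assumptions; none comes from the protocol. Let p be the share agreeing among those who needed registration, q the share of those answering who did not need it, and r the share of that second group who choose an agreeing option. Then

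observed agreement = p(1 − q) + rq.

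Take p = 60%.

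| q | r = 0 (all choose neutral, for example) | r = 1 (all choose agreement) |
|---|---|---|
| 10% | 0.60 × 0.90 = 54% | 0.54 + 0.10 = 64% |
| 30% | 0.60 × 0.70 = 42% | 0.42 + 0.30 = 72% |
| 50% | 0.60 × 0.50 = 30% | 0.30 + 0.50 = 80% |

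The same true value of 60% can appear lower or higher, and the closed answers reveal neither q nor r. Neither the size nor the direction of the distortion could be estimated from them.

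**The case against.** The strongest reply is that the protocol promises little. It calls the survey a first step based on respondents' experience and commits to no prevalence estimate. It does collect some facts, and opinion is half of what it set out to collect. On that view, coverage is thin rather than wrong. Part of this stands. A reader might infer that the form ignores current practice, or that 53% opinion items is itself a defect. The documents support neither: Q6 to Q10, Q14 and Q15 touch practice, and a large share of opinion items is compatible with the aim. What remains is that calling it a first step does not take current practice out of the aim, and on three named topics there is no closed practice item.

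A second reply is that the comment boxes allow a respondent to write that registration was not needed, or what was done about follow-up. They do, so the gap concerns the closed answers only. But the boxes ask for none of this, and silence in a box cannot be read as a no, so they give no reliable denominator. The possibility of later questions helps little: it depends on the respondent's approval, no item clearly records that approval, and no later questions are set out.

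Third, it is tempting to say that Q14 forces an answer. That is an inference from an undefined asterisk. It is plausible, but the supportable statement is that unsuitable respondents may be included.

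Finally, a reader might treat the missing year and length of the last mission, or the mixture of presence and value in Q15, as equal failures. They are weaker points. Q14 is the only existing item clearly affected by the lack of a date or length, and participation is not restricted to short missions. Q15 is worded about collaboration in general, so its not being tied to one mission fits its question; its mixed options are a separate wording matter.

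**Conclusion.** The point holds in a limited form. For 3 topics (Q17, Q18, Q19) the closed items cannot show whether the practice occurred, although current practice is a stated aim. For Q14, none of the 5 options identifies respondents to whom the question does not apply, so the ease rating may be contaminated by an unknown amount. The first conclusion rests only on the printed items. The second assumes that some respondents had a last mission without a registration requirement and answered Q14 all the same; the percentages shown for it are illustrative. The opinion half of the survey is unaffected and remains usable.

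**What to change.** 1. **Q14:** add an option such as *Not required at my last mission*, and report the ease rating only among respondents for whom registration was required.
2. **Q17, Q18, Q19:** beside each, add one factual question about the last mission the respondent took part in or hosted, answered *Yes / No / Don't know*: was such a follow-up plan in place; was such a report written (with *Not yet due* as a further option); was such a strategy in place.
3. **Reporting:** show these answers next to the endorsement figures, as proportions of respondents. They are not proportions of missions, since several respondents may describe the same one, and the form goes out only as stated: "June 2019, by email within the network of GSA and ICOPLAST".
4. **Consistency:** update both counts, "The survey consists of 21 questions" in the General information row and "The questionnaire consists of 21 questions" in the survey introduction.

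Cost: three short questions and one option. 21 + 3 = 24 numbered questions, and 3/21 = 14% more. The form is emailed and voluntary, so a small loss of completion is possible.

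If the form can no longer change, the remedy is wording only. Limit the objective and conclusions on follow-up, reporting and long-term strategy to respondents' opinions, and state that Q14 may include respondents for whom registration was not required. Asking for the year and duration of the last mission, and splitting Q15 into presence and value, are optional improvements.

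### The survey addresses visiting teams and host doctors but never asks respondents which they were, so the visitor/host mix is known only approximately; Q14 also lacks a not-applicable option

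*Protocol*

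**What the plan says.** The protocol describes a two-sided respondent population in three places. The title names "members of foreign teams and local doctors involved in surgical missions", the Participants row of the protocol table repeats it, and the questionnaire is headed "A survey for international and local team members involved in surgical missions in LMICs".

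The form opens with an unnumbered item on function, whose eight options are professions, NGO posts and a residual category. Numbered items follow: "The questionnaire consists of 21 questions".

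The items that bear on side are:
- "Q5. Nationality"
- "Q6. How many missions did you perform in your life"
- "Q7. Country where you performed your last surgical mission"
- Q8 and Q9, on the hospital and the NGO of that mission
- "Q10. Country where this NGO is based"

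Q14 puts a statement for agreement: "Q14. When medical registration was required for your last mission, the process to obtain the documents was straightforward". It has five agreement levels and a comment box.

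All of these items carry an asterisk, read here as marking a required answer.

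**The concern.** The General information row says that the answers will describe current practice and support recommendations. On several topics visitors and hosts stand in different positions: what a visiting team should do (Q11), registration in the host country (Q13), dealings with local authorities (Q15) and a jointly written strategy (Q19). A reader of pooled percentages on these items will want to know how much of the opinion is the visitors' and how much the hosts'. A form that does not ask cannot report this exactly.

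The wording of Q6 and Q7 adds to the difficulty. Both ask about missions that the respondent performed, which comes naturally to someone who travels and less so to someone who receives a team. Q14 raises a related question of fit: it requires an answer from people to whom it may not apply.

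**Working it through.** No sample-size or power calculation is involved. The check is an item count and a reading of what each item can reveal.

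**Item count.** Q1 to Q21 gives 21, which matches the stated number. Adding the unnumbered function item gives 21 + 1 = 22. Items that ask for visiting or host side: 0 of 22.

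**What the other items reveal.** Q7 to Q10 describe the mission: its country, hospital, NGO and the NGO's base. A visitor and a host who worked on the same mission, and who both answer for it, would give the same four answers. These items therefore separate the two only when set against facts about the respondent, namely nationality (Q5), name (Q1), email (Q4) and any comments. The simplest rule is: Q5 equal to Q7 means host, and Q5 different from Q7 means visitor.

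**The rule applied case by case**, with A and B as two countries and the mission in B:
- Visitor of nationality A: Q5 differs from Q7, classed visitor. Correct.
- Host of nationality B who answers Q7 with B: classed host. Correct.
- Diaspora visitor, nationality B but living in A: classed host. Wrong.
- Expatriate of nationality A employed at the hospital in B: classed visitor. Wrong.
- Host of nationality B who reads Q7 as missions travelled on and names a third country: classed visitor, although this is one of the local doctors whom the survey seeks.

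The first two cases are the typical ones, so the rule works for most respondents. An email domain, the hospital name or a comment may settle some of the others. The protocol contains nothing from which the frequency of the last three could be estimated.

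**Q6.** A local surgeon who has received ten visiting teams and never travelled could reasonably write 10 or 0. Unless the respondent explains, a count from a host and a count from a visitor may measure different things.

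**Q14.** The statement is conditional on registration having been required. Someone for whom it was not required, whether host or visitor, must still choose one of the five levels. If that is the middle one, it cannot be told from a genuinely neutral answer unless the respondent comments. A role item would not cure this, so it is a separate matter.

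**The case against.** The strongest reply is that no stated aim fails. The protocol announces no foreign-versus-local comparison, quota or subgroup, and the missing item leaves the pooled answers as they are. This stands, and it sets the severity.

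Second, the form already collects enough to classify most people, and name and email are required, so the investigators can look into doubtful cases. This also stands. A reader might infer that side is unrecoverable, or that the survey is invalid; the protocol supports neither. A later analysis plan could define the classification rule. It could not supply an answer that was never collected. The introduction to the questionnaire does foresee further questions to respondents who approve contact, but no item records that approval, since Q21 covers publication only. Recontact is therefore a partial remedy.

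Third, the heading addresses local team members, so a host may well read Q6 and Q7 as missions taken part in. That is plausible. The protocol does not show that hosts would misread the items; it only leaves both readings open.

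Fourth, Q14 has a neutral level and a comment box, and respondents are invited to clarify there. This softens the point, but the comment is optional and the agreement level is not. It would also be tempting to take Q14 as evidence of a visitor-only form. It is not, because a visitor whose mission needed no registration meets the same difficulty.

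**Conclusion.** The point holds as a cheap improvement of low severity. None of the 22 items records side directly. A usable proxy exists through Q5 and Q7, and it can misplace three identifiable kinds of respondent. The effect is mainly on description: the visitor/host mix behind the opinions and recommendations can be reported only approximately, and Q6 may not be comparable between the two groups. Q14 has a separate, smaller defect that affects either side.

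No numerical size can be given. Any figure for the distortion of the mix would follow entirely from assumed error rates and an assumed local share, for which the protocol offers no support. The conclusion rests on reading the asterisks as required answers and on the printed form being the one distributed, as the Study type row indicates.

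**What to change.** Before distribution, which the protocol sets for June 2019:
- Add one required item on role in the last mission: *visiting team*, *local or host team*, or *neither*. The third option serves respondents such as NGO policy officers and board members, whom the function item admits.
- Reword Q6 to ask for missions *you took part in (as visiting or host team)*.
- Reword Q7 to *country where your last mission took place*.
- Add *not applicable* to Q14.
- Report the role mix of respondents alongside the pooled results.

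If the new item is numbered, the stated total becomes 21 + 1 = 22, and both places that give it (the General information row and the questionnaire introduction) need updating.

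The cost is one extra tick-box, one extra response option and two rewordings, with no additional participants or staff. The downside is a slightly longer form. If the form has already gone out, the remaining course is to state the Q5-against-Q7 rule, say how doubtful cases were settled, and report the mix as approximate.

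### The survey addresses visiting teams and local doctors, but no item asks which the respondent was; Q11 also leaves its scoring rule and one row unclear

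*Protocol*

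**What the plan says.** The title, the Participants entry of the protocol's summary table and the heading above the questionnaire all describe a survey of two kinds of respondent: visitors and local staff. The Study type entry says that the survey's content is set out in the protocol itself, so the item wording belongs to this document.

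The opening item, "Your function", offers professions (nurse or physician assistant, several kinds of surgeon), two NGO posts (policy officer, board member) and an open *other* category. Place and affiliation are then asked as short free text: "Q5. Nationality", country of the last mission (Q7), hospital and town (Q8), supporting NGO (Q9) and the country where that NGO is based (Q10).

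Q11 reads "Q11. Please give points over the following potential activities of a visiting team". It sets four activities against four scores, 1 to 4 points. Its only scoring rule is "more points means a more important activity". The third row is "Treat patients yourself". The general instruction above the items is "Please select one answer, and further clarify in the comment box if applicable".

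**The concern.** The protocol defines its respondents by two groups and then does not record the group. Any description of who answered, and any reading of the answers by group, has to rest on inference. The two groups stand on different sides of a mission, and the summary table says that the answers will feed recommendations, so a reader of the results will want to know whose views they are.

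The Q11 points are secondary. If some respondents share out the scores 4, 3, 2 and 1 while others rate each row on its own, the same number of points does not mean the same thing for both. And if a local doctor takes the third row to refer to his or her own work, that row's score answers a different question from the one a visitor answered.

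A later analysis plan can choose how to summarise the answers, but it cannot change what was asked.

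**Working it through.** The protocol gives no figure on this point, so there is none to reproduce. The check sets the items side by side.

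**1. Can role be recovered from the items?** Neither the function item nor any of Q1 to Q21 asks whether the respondent was visiting or local. Q7 to Q10 describe the mission (country, hospital, NGO, NGO's country). A visitor and a local doctor on the same mission can therefore give identical answers to all four. Among the items on place and affiliation, only Q5 describes the respondent. The natural proxy is Q5 against Q7: same country means local, different country means visiting.

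| Respondent | Q5 against Q7 | Proxy says | Correct? |
|---|---|---|---|
| Foreign national, visiting | different | visiting | yes |
| Host-country national, working locally | same | local | yes |
| Host-country national, visiting with a foreign team | same | local | no |
| Foreign national, working locally | different | visiting | no |
| NGO policy officer or board member, on neither team | either | visiting or local | no |

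The proxy works in the two plain cases and fails in the other three. The document gives no frequencies, so the share misplaced is unknown.

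**2. Does Q11 fix its scoring rule?** Two features suggest a ranking: the wording about giving points over a list, and four scores for four activities. One feature suggests separate ratings: each row has its own set of four buttons, and nothing tells the respondent to use each score once. The general instruction to select one answer does not settle whether two rows may share a score. The readings differ as follows:

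- Ranking: every respondent's total is 1 + 2 + 3 + 4 = 10, and ties are impossible.
- Rating: a total may lie anywhere from 4 × 1 = 4 to 4 × 4 = 16, and ties are allowed.

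This shows that the scales differ. It does not show that any respondent was confused.

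**3. Does another item repair Q11?** Q13 to Q19 each carry a comment box; Q11 has none. The next item, "Q12. Is there, in your opinion, an activity missing in question 11? (please explain what activity is important and why", gives room to write but asks about activities left off the list, not about how the grid was read.

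**4. Does the third row fit the stem?** The stem concerns the activities of a visiting team. The third row is the only one that uses the second person. For a visitor, stem and row agree. For a local doctor, the row can mean treatment by the visitors (following the stem) or by the respondent (following the row).

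**The case against.** The strongest reply is that nothing declared depends on these points. The protocol announces no comparison of the two groups and no summary of Q11. This stands: no stated analysis fails. A reader might infer that a planned comparison of visitors and local doctors is invalidated, but the document plans none, and one may or may not appear in an analysis plan that is not shown.

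Second, Q11 as printed looks like a rating, and the online form may have limited each score to one use or shown plainly that scores could repeat. The text cannot show how the form behaved. This also stands. A reader might infer that rankings and ratings were in fact mixed and that pooled points would put the activities in the wrong order. The document does not support that: it shows an open instruction, not confusion and not a reversal. Nor should one go to the other extreme and assume that each respondent's order is intact under either reading, because ratings can contain ties that a ranking would have forced apart.

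Third, the stem is a strong cue for the third row, and the contrast with the row on teaching local staff makes the intended meaning fairly clear. This reduces the row to a matter of clarity for local doctors.

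Fourth, name (Q1) and email address (Q4) are asked, so respondents could be contacted. This stands in part. The protocol says "we may ask additional questions in the future if you approve us to contact you", so contact depends on approval, and no printed item records that approval; Q21 concerns consent to publication only.

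What remains is that a basic descriptor of the respondents is not asked directly, and that two pieces of wording in Q11 can be read in two ways.

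**Conclusion.** The point holds as a minor, cheap improvement. The missing role item is the main part: the protocol names two groups and offers only an indirect, free-text proxy for telling them apart. The Q11 scoring rule and the third row are secondary.

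No size is claimed for any of the three. The document gives neither the share of respondents whom the proxy would misplace, nor how many took Q11 as a ranking, nor how many local doctors read the third row literally. The conclusion rests on the questionnaire as printed, and on the assumption that the online form added no role question, no limit on repeated scores and no further explanation.

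**What to change.** **Before answers are collected**

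- Add one required tick-box: *On your last mission, were you: a visiting team member / a local team member / neither (for example, an NGO policy or board role)?* Describe respondents by this answer. The third option is needed because the function item admits NGO policy officers and board members, whom a forced two-way choice would misplace.
- Add to the Q11 stem: *Rate each activity separately; scores may repeat.* This matches the grid as printed.
- Reword the third row: *Visiting team members treat patients themselves.*

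**If answers were already collected with the present wording** (the summary table has distribution starting in June 2019 and enrolment ending in October 2019)

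- Summarise Q11 by the order of activities within each respondent, with ties allowed.
- Classify role from Q5 and Q7 to Q10, and state that this is approximate.
- Put the role question to those who approved further contact.

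This repair is partial: ties that a respondent felt obliged to break cannot be recovered, and role stays inferred for anyone who cannot be contacted.

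**Cost.** One extra item, one line in the stem and one reworded row. Ratings may cluster at the top and separate the activities less. A forced ranking would avoid that, but a respondent who finds all four activities essential could then not say so.
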